2.0 RATIONALE

A recent service evaluation was conducted to compare the number of diagnoses of disorders of rectal sensitivity (n=70 per site) across NUTH and CDDFT services, in order to identify whether both pieces of equipment produce similar proportions. In NUTH, the majority of patients (91.4%) were diagnosed as normal, whereas in CDDFT, the majority of patients (65.7%) were diagnosed with rectal hypersensitivity. This suggests a possible difference in how each piece of equipment classifies patients, although the limitations such as two different cohorts of patients being studied, and the relatively small sample size should be acknowledged. This service evaluation supported the need for more research into our normal values and how we assess rectal sensitivity, and questioned whether a rectal barostat could be more appropriate.

There is little research directly comparing the assessment of rectal sensitivity using elastic balloon distension and the rectal barostat. A study by Sauter et al. (2014) assessed 26 healthy volunteers using both the elastic balloon inflation and barostat methodologies to assess rectal sensitivities, by recording volume inflated at first sensation, normal urge, and

sustained urgency. They found there was no agreement between the elastic balloon and barostat recorded volumes, however, this is possibly due to the difference in physical properties and shape at identical volumes, which the study failed to take into account^[12]. There are currently no studies comparing the two devices in a symptomatic population, and no indication whether patients receive different diagnoses depending on what device is used to assess rectal sensitivity. Accurate and comprehensive assessment of disorders of rectal sensation to distension in symptomatic patients is vital, as studies have suggested patients with rectal hyposensitivity treated with biofeedback therapy improved their sensory thresholds and symptom severity^[14], and sensory retraining is of greater utility when treating faecal incontinence than strength training alone^[15].

This feasibility study will help investigate key variables required to inform a future definitive study, which will aim to determine whether patients receive a different diagnosis of rectal sensitivity dependent upon the test used. Moreover, a definitive study will address the potential impact of rectal sensitivity testing methodologies on patient outcomes.

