3.2 Secondary Objectives

- To assess whether they are any differences in rectal sensitivity diagnoses when using the London classification between the two methodologies (elastic balloon distension test and rectal Barostat test).
- To assess the repeatability of the rectal barostat test.
- To investigate whether patients with larger rectums require the elastic balloon to be inflated to a larger volume, before they feel an urge to defecate.
- To determine whether the Laborie elastic balloon test or Medtronic elastic balloon test aligns better with the rectal barostat test.
- To assess study participant eligibility, uptake and drop-out rate.
- To assess study acceptability and tolerability.
- To assess the costs per study of the two methodologies to help inform a definitive study (clinic time, analysis time and consumables).

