3.3 Outcome Measures

As this is a feasibility study, there are no primary outcome measures, only secondary outcome measures. These include:

- The London Classification diagnoses of each patient when rectal sensitivities are assessed using Laborie system elastic balloon distension versus the rectal barostat, and Medtronic system elastic balloon distension versus the rectal barostat.
- Percentage of rectal capacity at each sensory threshold per test will be measured to assess repeatability
- Total rectal volume (mL) measured using the rectal barostat will be recorded to assess correlation between capacity and balloon inflation (mL) at sustained urgency.
- The number of patients who were eligible to participate in the study.
- The number of patients who chose to participate in the study.
- The number of patients who dropped out of the study.
- The length of time required for the rectal barostat protocol and the elastic balloon distension protocol in clinic
- Costings of rectal barostat test comparison (costs of barostat bags and any additional staff time required)
- Study acceptability and tolerability assessment.

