6.3 Number of Participants

In total 30 participants will be recruited for the study. 15 participants will be recruited at NuTH and 15 at CDDFT. Study recruitment will continue until complete study data has been obtained from 15 participants at each site.

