7.8 Data Analysis

To investigate whether London Classification diagnoses differs when using the rectal barostat compared to elastic balloon distension, a binary indicator will be used to determine the percentage of patients who's diagnoses were in agreement. To examine this closer, a Fisher's exact test will be used to determine whether the difference in number of diagnoses between the elastic balloon distension and rectal barostat reaches a significance level of p=0.05.

To assess repeatability of sensory thresholds at first sensation, normal urge, and sustained urgency of the rectal barostat, an intraclass correlation coefficient will be calculated for each test.

To identify whether there is a correlation between total rectal capacity and the volume of the elastic balloon at the sensory threshold of sustained urgency, a Pearson's correlation will be calculated to test the strength of the relationship between these variables.

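### Section 7.8 compares diagnoses for elastic balloon against barostat without splitting by balloon system, although sections 3.2 and 3.3 define the question per system

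*Protocol*

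**What the plan says.** Section 3.3, repeated in the study summary, sets the diagnosis outcome as the London Classification result under "Laborie system elastic balloon distension versus the rectal barostat, and Medtronic system elastic balloon distension versus the rectal barostat". Section 3.2 has a matching objective: "To determine whether the Laborie elastic balloon test or Medtronic elastic balloon test aligns better with the rectal barostat test".

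Section 7.8 does not carry that split forward. It says first that "a binary indicator will be used to determine the percentage of patients who's diagnoses were in agreement". It then adds one Fisher's exact test, whose stated purpose is this: "determine whether the difference in number of diagnoses between the elastic balloon distension and rectal barostat reaches a significance level of p=0.05". No system, site or stratum is named in either sentence, and nothing in 7.8 addresses which system aligns better.

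System is fixed by site. Section 7.5.3 assigns Laborie to NUTH and Medtronic to CDDFT, section 5.0 keeps patients at their own site, and section 6.3 says "15 participants will be recruited at NuTH and 15 at CDDFT". A single test over all patients would therefore mix the two systems half and half.

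The protocol gives reasons to keep them apart. Section 1.0 says that the systems use different published normal ranges. Section 2.0 reports, from 70 patients per site: "In NUTH, the majority of patients (91.4%) were diagnosed as normal, whereas in CDDFT, the majority of patients (65.7%) were diagnosed with rectal hypersensitivity".

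**The concern.** The analysis in 7.8 does not match the outcome in 3.3 and leaves one objective in 3.2 without an analysis. Two things follow if 7.8 is carried out as a single comparison.

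First, the Fisher test compares numbers of diagnoses, which is a net quantity. If one balloon system gives fewer hypersensitive diagnoses than the barostat and the other gives more, the two shifts offset each other in the total. The p-value can then suggest that balloon and barostat agree when neither system does.

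Second, one agreement percentage over 30 patients cannot say whether disagreement comes from Laborie, from Medtronic or from both. That is what the study asks, and it is what a definitive study would need to know.

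This is separate from the choice of an unpaired test for paired data. A paired test on the pooled counts nets opposite shifts in the same way.

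**Working it through.** The protocol states no power, effect size or sample-size derivation, so there is no planned figure to reproduce. The service-evaluation percentages are consistent with whole counts: 64/70 = 91.4% and 46/70 = 65.7%.

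**Inputs**
- 15 patients per system, 30 in total (section 6.3).
- Hypersensitive on Laborie: at most 6/70 = 8.6%, because 64/70 were normal (section 2.0).
- Hypersensitive on Medtronic: 46/70 = 65.7% (section 2.0).
- Hypersensitive on barostat, q: not given in the protocol. Assumed equal at both sites and varied from 10% to 60%.
- Two-sided tests assumed, since 7.8 does not state sidedness. The four diagnoses are reduced to hypersensitive or not.

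**Step 1: cancellation in counts, extreme case**
- Laborie 0/15 v barostat 8/15. Two-sided Fisher p = 2 × C(15,8)/C(30,8) = 2 × 6,435/5,852,925 = 0.002.
- Medtronic 15/15 v barostat 8/15. Two-sided Fisher p = 2 × C(15,7)/C(30,7) = 2 × 6,435/2,035,800 = 0.006.
- Pooled: (0+15)/30 v (8+8)/30 = 15/30 v 16/30, p = 1.0.

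Two clear differences in opposite directions disappear in the total. At least 8 + 7 = 15 of the 30 patients have changed diagnosis, so agreement is at most 50%.

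**Step 2: counts near the service-evaluation rates**
- Laborie 1/15 v barostat 5/15: p = 0.17.
- Medtronic 10/15 v barostat 6/15: p = 0.27.
- Pooled: 11/30 v 11/30, p = 1.0.
- At least 4 + 4 = 8 of 30 patients are discordant, so agreement is at most 22/30 = 73%.

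**Step 3: how often each Fisher test reaches p ≤ 0.05**

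Simulation of 20,000 trials per value of q, with the smallest possible within-patient discordance. Each patient has one uniform rank u. The barostat is positive if u < q, and the balloon is positive if u < 0.086 (Laborie) or u < 0.657 (Medtronic).

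| Barostat rate q | Laborie alone | Medtronic alone | Pooled |
|---|---|---|---|
| 10% | 0% | 87% | 68% |
| 20% | 1% | 60% | 14% |
| 30% | 11% | 27% | 1% |
| 37% | 26% | 11% | about 0.1% or less |
| 45% | 46% | 3% | 0.5% |
| 60% | 81% | 0% | 23% |

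With an exact McNemar test at q = 37%, the pooled test reaches p ≤ 0.05 in 0.6% of trials, against 24% for each system. Pairing does not remove the cancellation.

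**Step 4: per-patient agreement in the same model**

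For q between the two balloon rates, the expected discordant share is ½(q − 0.086) + ½(0.657 − q) = ½ × 0.571 = 0.286, whatever q is. Expected agreement is therefore about 71%, and the simulation gives the same value. This measure does not cancel.

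**The case against.** Four arguments on the other side have weight.

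*Section 7.8 never says that the systems are pooled.* This is true. It uses the generic term, as the first objective in 3.2 does, and a statistical analysis plan could apply the test by system. What stands against this is that the protocol itself fixes a contrast, a test and a threshold without naming a system. One combined test is the natural reading, and that does not match 3.3.

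*The agreement percentage comes first in 7.8 and cannot cancel.* This stands. A reader might infer that the study would report no difference between the methods. The documents do not support that: about 71% agreement would appear beside the p-value, so only the Fisher result would mislead.

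*Opposite errors are assumed.* This also stands. Section 2.0 acknowledges that the two sites studied different cohorts in small numbers, and that evaluation gives no barostat results. It suggests that the systems may differ from each other, not that they err on opposite sides of the barostat. At a barostat rate of 10% there is almost no cancellation, and the pooled Fisher test detects a difference in 68% of trials.

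*Splitting does not rescue the test.* At q = 37%, neither per-system Fisher test is significant in about 67% of trials. This limits what the split can achieve through p-values, but not through estimates.

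A reader might also infer that testing each system and the pool at 0.05 would about double the error rate. No passage plans three tests. With these conservative exact tests, the simulated family-wise rate for all three contrasts was 0.2% to 5.0%, so that argument is not made here.

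**Conclusion.** The mismatch is real on the text. Sections 3.2 and 3.3 ask about each balloon system, 7.8 specifies one undivided comparison, and the objective of finding the better-aligned system has no analysis in 7.8.

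The possible damage to the Fisher test is large when the barostat rate lies well between the two systems' rates. From 30% to 45%, the pooled test is significant in 1% of trials or fewer, although about 29% of patients change diagnosis. Outside that range the loss is smaller. These figures rest on four assumptions: a common barostat rate at both sites, the service-evaluation rates carrying over to the study, minimum discordance, and a two-category outcome. They show what could happen and do not predict what will.

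The consequence is confined to the Fisher p-value and to the inability of an undivided percentage to locate the disagreement. The point is worth correcting because the correction is nearly free. It does not show that the study as a whole would reach a false conclusion.

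**What to change.** Amend 7.8 to follow 3.3. State that the diagnosis comparison is made separately for Laborie v barostat (n=15) and Medtronic v barostat (n=15). For each system, report:
- the 4×4 cross-table of balloon diagnosis by barostat diagnosis;
- the percentage agreement with its 95% CI;
- the direction of change, for example hypersensitive on balloon only against hypersensitive on barostat only.

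Add that no conclusion is drawn from diagnosis counts pooled over the two systems. The two sets of estimates side by side also give the objective on which system aligns better an analysis.

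The cost is a wording change, with no new data or patients. The downside is precision. With 15 patients, the approximate half-width of a 95% CI is 1.96 × √(0.7 × 0.3/15) = 23 points at 70% agreement and 1.96 × √(0.8 × 0.2/15) = 20 points at 80%. Per-system tests will often be non-significant, so the reading should rest on the estimates and their intervals.

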7.5.3 Anorectal Manometry and Rectal Sensitivity Testing

Participants from NUTH will have anorectal manometry and rectal sensitivity tests as per local procedure using a Laborie Solar High Resolution Manometry System with water-perfused catheters. Participants from CDDFT will have anorectal manometry and rectal sensitivity tests as per local procedure using a Medtronic 3D Solid-State

High Resolution Manometry System. These tests are performed as per standard care, however rectal sensitivity testing will be performed twice more as part of non-standard care.

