7.5.4 Rectal Barostat

Participants from NUTH and CDDFT will have the rectal barostat test performed as per local procedure as part of non-standard care.

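### Barostat repeatability rests on an intraclass correlation alone, which does not show how far one patient's threshold moves between runs

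*Protocol*

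**What the plan says.** Section 3.2 sets the objective: "To assess the repeatability of the rectal barostat test". Section 3.3 defines the outcome and its unit: "Percentage of rectal capacity at each sensory threshold per test will be measured to assess repeatability". Section 7.8 gives the analysis. It begins "To assess repeatability of sensory thresholds at first sensation, normal urge, and sustained urgency of the rectal barostat" and ends with the chosen statistic: "an intraclass correlation coefficient will be calculated for each test". No measure of error in the units of the threshold is named beside it, and no value of the ICC is set as acceptable.

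On the sample, section 6.3 states "15 participants will be recruited at NuTH and 15 at CDDFT". Section 6.1 admits patients with constipation or evacuation disorder, incontinence, anorectal pain, urgency or a constant urge. Section 1.0 describes both hyposensitive and hypersensitive patients, and both highly compliant and low-capacity rectums, among such disorders.

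On repeat runs, section 7.5.4 says only "Participants from NUTH and CDDFT will have the rectal barostat test performed as per local procedure", as part of non-standard care. The one statement about repetition is in section 7.5.3, on the manometry systems: "rectal sensitivity testing will be performed twice more as part of non-standard care".

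**The concern.** Repeatability asks how far the same patient's threshold moves when the test is run again. The ICC answers a different question: what share of the total variation comes from differences between patients. It rises when patients differ more, even if the barostat's run-to-run error is unchanged, and this study's eligibility criteria make a wide spread plausible.

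What is at stake is the interpretation of the device comparison. The study asks whether a patient's London Classification diagnosis changes with the device, and a diagnosis depends on where a threshold falls. Without the barostat's own within-patient error in threshold units, a disagreement between balloon and barostat cannot be separated from ordinary variation between two barostat runs. A feasibility study meant to supply key quantities for a definitive study should report that error.

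**Working it through.** The protocol states no ICC target, SD or sample-size derivation for repeatability, so there is no figure of its own to reproduce. The calculation shows how the ICC behaves under stated assumptions.

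**Inputs from the protocol.** 30 participants, 15 per site (section 6.3); outcome in percentage of rectal capacity (section 3.3).

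**Assumed, because the protocol gives none.** Within-patient SD *sw* = 10 percentage points; between-patient SD *sb* from 5 to 30 points; 2 or 3 runs per patient.

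**Step 1. Run-to-run error.** Repeatability coefficient = 1.96 × √2 × *sw* = 1.96 × 1.414 × 10 = 27.7 points. Two runs on one patient would differ by less than this about 95% of the time. It does not involve *sb*.

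**Step 2. ICC for that same error.** ICC = *sb*² / (*sb*² + *sw*²).

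| *sb* (points) | ICC | Repeatability coefficient (points) |
|---|---|---|
| 5 | 25/125 = 0.20 | 27.7 |
| 10 | 100/200 = 0.50 | 27.7 |
| 15 | 225/325 = 0.69 | 27.7 |
| 20 | 400/500 = 0.80 | 27.7 |
| 30 | 900/1000 = 0.90 | 27.7 |

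The ICC depends only on the ratio *sb*/*sw*. A ratio of 1, 2 or 3 gives 0.50, 0.80 or 0.90 whatever *sw* is, so the pattern does not hang on the assumed 10 points.

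**Step 3. The reverse reading.** One ICC is compatible with very different errors. An ICC of 0.80 arises from *sb* = 10 with *sw* = 5 (100/125) and from *sb* = 30 with *sw* = 15 (900/1125). The repeatability coefficients are 1.96 × 1.414 × 5 = 13.9 points and 1.96 × 1.414 × 15 = 41.6 points.

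**Step 4. Precision at this sample size.** The relative 95% half-width of the within-patient SD is about 1.96/√(2n(k−1)), for n patients and k runs:

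- n = 30: 1.96/√60 = ±25% with 2 runs; 1.96/√120 = ±18% with 3 runs.
- n = 15 (one site): 1.96/√30 = ±36% with 2 runs; 1.96/√60 = ±25% with 3 runs.

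For comparison, the exact F-based 95% CI around an observed one-way ICC of 0.80 with 2 runs is 0.62 to 0.90 for n = 30 and 0.51 to 0.93 for n = 15. The within-patient SD can be estimated usefully from all 30 patients; results by site are descriptive only.

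**The case against.** The ICC is a recognised reliability index. The mixed group is the population referred for the test, so reliability in that group is a legitimate quantity. Repeatability is one of seven secondary objectives in a 30-patient feasibility study, and no pass mark or progression decision depends on the ICC. All of this stands, and it limits the point to sole reliance on the ICC. It does not remove it: section 7.8 has selected the statistic, and that statistic cannot give the size of run-to-run movement.

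Three stronger readings are tempting, and the documents do not support them.

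- **That the ICC is inflated by pooling two differing sites.** Section 7.8 does not say whether sites are combined. If they were, a difference *d* between site means would add *d*²/4 to the between-patient variance: with *sb* = *sw* = 10, an assumed *d* of 20 would move the ICC from 100/200 = 0.50 to 200/300 = 0.67. But no barostat mean or SD is given for either site. The contrast in section 2.0, "In NUTH, the majority of patients (91.4%) were diagnosed as normal, whereas in CDDFT, the majority of patients (65.7%) were diagnosed with rectal hypersensitivity", comes from the existing balloon equipment in different cohorts. Section 2.0 itself warns of this, and section 1.0 adds that the two systems use different normal ranges. It is not evidence of a barostat difference between sites.
- **That the ICC would miss a systematic shift between runs.** That is true of a consistency-type ICC, but the protocol does not choose that form. The form, the model and the confidence interval may be settled in an analysis plan that is not shown.
- **That the barostat is not repeatable, or that the study will misreport it.** There are no data on this. A high ICC alongside large error is a possibility, not a demonstrated result.

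**Conclusion.** The point holds as an improvement at almost no cost, not as an error in using an ICC. As the only statistic fixed for this objective, the ICC mixes patient spread with measurement error. For an unchanged repeatability coefficient of 27.7 points it can lie anywhere from 0.20 to 0.90 over the assumed range of spread. The dependence on spread is a property of the formula; the figures in points rest on the assumed within-patient SD of 10. How large the actual error will be cannot be known from the protocol.

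The argument needs neither pooling of sites nor any particular form of ICC. It does need repeated barostat runs, which the protocol does not clearly provide: section 7.5.4 mentions none, and the additional testing in section 7.5.3 is placed under the manometry systems. Without repeat runs, neither the ICC nor the measures proposed here can be calculated.

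**What to change.** In section 7.8, for each of the three sensory thresholds on the barostat:

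1. Report the mean run-to-run change with 95% CI.
2. Report the within-patient SD with the repeatability coefficient (1.96 × √2 × within-patient SD), or Bland-Altman limits of agreement.
3. Give both in percentage of rectal capacity, the unit of section 3.3, with mL as an addition.
4. Base the repeatability conclusion on items 1 and 2, and keep the ICC with its 95% CI beside them.
5. If data from both sites are combined, also show the results by site, labelled as descriptive (15 patients each).

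Sections 7.5.3 and 7.5.4 must be reconciled with the repeatability objective on whether repeat barostat runs take place; which arrangement is right is for the study team.

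The cost of items 1 to 5 is a few lines of text. Where the barostat is repeated, they use the same readings that the ICC requires and no further data.

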The most common assessment of rectal sensitivity in a clinical environment is made by gradually inflating an elastic balloon within the rectum, and measuring the volumes at which the patient reports their first sensation, their normal urge to defecate, and sustained urgency^[7]. This is commonly performed in conjunction to anorectal manometry (ARM), which involves insertion of a catheter into the anorectum, and measuring pressure at rest and during specific manoeuvres to assess the function of the anal sphincters^[8]. Most commercially available catheters for this test also contain the required elastic balloon to assess rectal sensitivities, which can be inflated manually or automatically by the equipment, depending on the model and the manufacturer. The advantages of assessing rectal sensitivities using the elastic balloon in conjunction with ARM is that it is fast and cheap, as it does not require a separate catheter being inserted for the additional test. However, the elastic properties of the balloon mean it is unsuitable to assess rectal compliance^[9]. In our

Study protocol: Assessing rectal sensitivity with elastic balloon distension versus rectal barostat.

services, we use two anorectal manometry systems across NUTH and CDDFT services. In NUTH we use a Laborie Solar High Resolution Manometry System with water-perfused catheters, and in CDDFT we use a Medtronic 3D Solid-State High Resolution Manometry System. Both systems are commercially available across the UK, and use a similar elastic balloon for inflation, however, they utilise different published normal ranges of sensory thresholds.

The rectal barostat is another, more comprehensive, device used to assess rectal sensitivity. It contains a polyethylene bag, which is inserted into the patient's rectum and inflated using a pneumatic pump either continuously or in phasic intervals^[10]. Unlike the elastic balloon, the rectal barostat bag has infinite compliance whilst filling, which allows measurement of rectal compliance and total rectal volume, due to its ability to measure opposing pressure of the rectal wall. This protocol is more time-consuming, and for this reason is not routinely used in clinical practice, however it is considered the gold-standard of assessing sensory thresholds, and has the advantage of adding additional information about the biomechanical properties of the rectal wall^[3].

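### The capacity objective concerns the urge to defecate, but the planned correlation uses only sustained urgency and does not say how the two sites' balloon systems are handled

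*Protocol*

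**What the plan says.** The objective in section 3.2, repeated in the Study Summary, reads: "To investigate whether patients with larger rectums require the elastic balloon to be inflated to a larger volume, before they feel an urge to defecate".

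The Background (section 1.0) describes the usual elastic balloon test as recording the volumes at which "the patient reports their first sensation, their normal urge to defecate, and sustained urgency". These are three separate thresholds. Section 7.8 names the same three when it describes the repeatability analysis of the barostat.

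The outcome measure in section 3.3, also in the Study Summary, is: "Total rectal volume (mL) measured using the rectal barostat will be recorded to assess correlation between capacity and balloon inflation (mL) at sustained urgency". Section 7.8 analyses the "correlation between total rectal capacity and the volume of the elastic balloon at the sensory threshold of sustained urgency" and says that "a Pearson's correlation will be calculated to test the strength of the relationship between these variables".

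Section 6.3 plans 15 participants at each of two sites. Section 7.5.3 gives the Laborie system to one site and the Medtronic system to the other, and section 5.0 says that patients are tested at the site where they are identified. Section 3.3 separates the two systems for the diagnosis outcome but not for the capacity outcome.

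**The concern.** There are two linked difficulties.

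First, the objective asks about the volume needed before an urge to defecate is felt. In the protocol's own list, the threshold that carries those words is normal urge. The only correlation planned is at the later-listed threshold, sustained urgency. As written, the objective could be reported as answered from a threshold that it does not name, with nothing reported at the one it most resembles.

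Second, balloon system is completely confounded with site, and section 2.0 itself raises a possible difference between systems or cohorts. A single coefficient that ignores site mixes the relation within sites, which is what the objective asks about, with any difference between site means. The result could partly reflect which hospital a patient attended. Since the study is meant to inform a definitive one, the answer on capacity should be free of that ambiguity.

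**Working it through.** **Threshold.** The passages side by side:

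| Place | Threshold named |
|---|---|
| Objective (3.2, Study Summary) | an urge to defecate, unqualified |
| Background (1.0) | first sensation; normal urge to defecate; sustained urgency |
| Outcome measure (3.3, Study Summary) | sustained urgency |
| Analysis (7.8) | sustained urgency |

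Outcome measure and analysis agree with each other. Both differ from the objective on its closest reading. No arithmetic applies here.

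**Site.** The protocol gives no expected correlation, power or SD for this analysis, so there is no figure of its own to reproduce. Its only relevant number is 15 + 15 = 30. Every correlation and shift below is an assumption.

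Take two equal groups with within-site SD 1 and within-site correlation rho. Let the site means differ by d SD in balloon volume and by c SD in capacity. Each site mean lies d/2 (or c/2) from the overall mean, so the site difference adds d²/4 and c²/4 to the two variances and dc/4 to the covariance:

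pooled r = (rho + dc/4) / sqrt((1 + d²/4)(1 + c²/4))

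Only balloon volume shifts (c = 0), rho = 0.50:

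- d = 0.5: 0.50 / sqrt(1.0625) = 0.49
- d = 1: 0.50 / sqrt(1.25) = 0.45
- d = 1.5: 0.50 / sqrt(1.5625) = 0.40
- d = 2: 0.50 / sqrt(2) = 0.35

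Both variables shift, rho = 0.50, d = 1:

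- c = +0.5: (0.50 + 0.125) / sqrt(1.25 × 1.0625) = 0.54
- c = −0.5: (0.50 − 0.125) / sqrt(1.25 × 1.0625) = 0.33
- c = +1: (0.50 + 0.25) / 1.25 = 0.60

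True correlation zero (rho = 0):

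- c = 0: pooled r is 0 whatever the value of d
- d = 1, c = ±0.5: ±0.125 / sqrt(1.25 × 1.0625) = ±0.11
- d = 1, c = 1: 0.25 / 1.25 = 0.20

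So ignoring site can dilute, inflate or create a correlation, depending on shifts that are not known.

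**Price of adjusting for site.** The Fisher-z interval is tanh(atanh(r) ± 1.96 × SE), at an assumed r of 0.50, for which atanh(r) = 0.549:

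- one unadjusted coefficient, n = 30: SE = 1/sqrt(27), 95% CI 0.17 to 0.73
- one site-adjusted (partial) coefficient, n = 30: SE = 1/sqrt(26), 95% CI 0.16 to 0.73
- a separate coefficient in each site, n = 15: SE = 1/sqrt(12), 95% CI −0.02 to 0.81

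Adjustment costs almost no precision. Relying on two separate coefficients would cost a good deal.

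**The case against.** The case on the other side has real force.

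- **The objective's wording is generic.** It does not say normal urge, and an unqualified urge could cover sustained urgency. Outcome measure and analysis are consistent, so the variable is prespecified. This stands to the extent that nothing shows which threshold was intended. It does not remove the need to reconcile the sections.
- **Pooling is inferred.** Section 7.8 speaks of one coefficient and one balloon in the singular. It neither states that sites are pooled nor rules out adjustment, and a statistical analysis plan that is not shown may settle the matter. This stands, and the site part is therefore conditional on the natural reading. A later plan would be less able to settle the threshold mismatch, because the protocol fixes both the objective and the outcome measure.
- **The shifts have no source.** The service evaluation in section 2.0 (91.4% normal at one site, 65.7% hypersensitive at the other) reports diagnoses, in different cohorts, and the Background says the systems use different normal ranges. Different normal ranges change classifications, not millilitres, and the Background calls the balloons similar. Nothing suggests that barostat capacity differs by site, and without that a true zero stays zero. All of this stands.

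A reader might also infer that sustained urgency lies near the limit of tolerance and so partly measures capacity itself. The protocol does not define sustained urgency that way, so this argument is not available. Nor does it give any distributional information that would make Pearson's coefficient a wrong choice; a preference for a rank correlation would be no more than that.

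**Conclusion.** The point holds in a limited form. Objective and analysis name different thresholds on the closest reading, and no correlation is planned at normal urge. A reader might go further and say that the analysis uses the wrong threshold. The protocol does not support that, because the objective's wording may be what needs correcting.

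On site, a single unadjusted coefficient is open to distortion in either direction. At a true 0.50, the combinations worked above give pooled values from 0.33 to 0.60; at a true 0, they run from −0.11 to 0.20. These figures assume equal groups, a common within-site correlation and the stated shifts, none of which can be estimated from the protocol. They show what could happen and are not evidence that the result will be biased.

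The consequence is modest: this is a secondary objective of a 30-patient feasibility study, and no sample size or decision rule rests on it. The change is still worth making because it is nearly free.

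**What to change.** - In sections 3.2, 3.3 and 7.8, and in the Study Summary, reconcile the threshold. Either correlate capacity with elastic balloon volume at normal urge and at sustained urgency, or reword the objective to sustained urgency if that was intended.
- In section 7.8, state that the correlation is adjusted for site, by partial correlation or by regressing balloon volume on capacity with a site term, and is reported with a 95% CI. Show the data by site, as description only, since 15 patients per site give wide intervals.

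The cost is wording and one degree of freedom. Site is known for every patient. Balloon volume at normal urge is probably recorded already, since the Background describes it as part of the usual test, but section 7.5.3 defers to local procedure, so it should be confirmed that the CRF captures it at both sites.
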